### 13.3. Secondary Endpoints:

Analysis plan for Secondary Endpoints: We will report the sensitivity, specificity, positive and negative predictive value of  $^{68}\text{Ga}$  PSMA-HBED-CC PET/CT over all imaged regions as well as sub-classified by the following regions:

- extra-pelvic nodal metastases
- visceral metastases
- osseous metastases

No statistical significance will be generated due to the pilot nature of the project.

Follow-up for extra-pelvic nodal metastases, visceral metastases and osseous metastases are defined as below:

13.3.1. True positive region

13.3.1.1.  **$^{68}\text{Ga}$  PSMA-HBED-CC PET/CT positive for extra-pelvic node metastases by internal blind reader** – and pathology (if available) positive for that node, or, extra-pelvic node positive for disease by imaging as defined in Section 12.2.2.1.

13.3.1.2.  **$^{68}\text{Ga}$  PSMA-HBED-CC PET/CT positive for visceral metastases by internal blind reader** – and pathology (if available) positive for that visceral lesion, or, visceral lesion positive for disease by imaging as defined in Section 12.2.2.2.

13.3.1.3.  **$^{68}\text{Ga}$  PSMA-HBED-CC PET/CT positive for osseous metastases by internal blind reader** - and pathology (if available) positive for that osseous lesion, or, osseous lesion

positive for disease by imaging as defined in Section 12.2.2.3.

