## 12.2. Reference standard definition:

12.2.1. Histopathology/Biopsy will be the primary determinate of tissue positivity and negativity for prostate cancer disease. Pathology date, organ, and location as well as any notes related to the pathology will be obtained from the subject chart. The anatomical region/sub-region the pathology occurred in will be assigned by the investigator team:

Ga-PSMA-HBED-CC positive findings are aimed to be confirmed by histopathology/biopsy if clinically feasible. Pathology performed 60 days before or after the Ga-PSMA-HBED-CC PET will be available for correlation.

Histopathological procedures and biopsies will be performed as clinically indicated and as per institutional protocol.

12.2.1.1. Lymph Nodes, Visceral Lesions, and Bone Lesions positive for disease by pathology.

- Lesions with positive pathologic confirmation will be regarded as positive for disease. The regionality of the resected tissue will be assigned into respective regions and sub-regions as described above in Table 12.2.

12.2.1.2. Lymph Nodes and Visceral Lesions negative for disease by pathology.

- Tissue removed and negative for pathology are considered negative for prostate cancer disease, unless subsequent conventional imaging or Ga-PSMA-HBED-CC PET imaging demonstrates that targeted tissue were not resected. In this case:

- i. Subjects can be rescanned with dedicated CT, MRI, or Ga-PSMA-HBED-CC PET/CT to determine if the suspicious Ga-PSMA-HBED-CC tissue was removed. If the tissue is confirmed as removed, this is considered negative for disease.

ii. If  $^{68}\text{Ga}$ -PSMA-HBED-CC PET/CT positive tissue is still present, a needle biopsy can be pursued at the discretion of the treating physician. Images of the procedure will be reviewed to determine if the correct tissue was biopsied.

- If the  $^{68}\text{Ga}$ -PSMA-HBED-CC PET/CT positive tissue was biopsied, a negative pathologic finding of the biopsied tissue is considered negative for disease.
- If the  $^{68}\text{Ga}$ -PSMA-HBED-CC PET/CT positive tissue was biopsied, a positive pathologic finding of the biopsied tissue is considered positive for disease.
- If biopsy or re-biopsy is not performed, or the wrong tissue was biopsied, change in node size as measured by conventional imaging and as defined below will be the criteria by which disease status will be defined.

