12.2.1.3. Bone lesions: Given the high rate of false negative biopsies for osseous metastases in subjects with prostate cancer, subjects with negative bone biopsies of  $^{68}\text{Ga}$ -PSMA-HBED-CC PET positive lesions will be further evaluated:

- If pathology demonstrates an alternative diagnoses that is known to be  $^{68}\text{Ga}$ -PSMA-HBED-CC positive (eg Renal Cell Carcinoma metastases, Paget's disease), then this will be considered negative for disease.
- If pathology is indeterminate, then follow-up imaging as described below will be performed as per clinical standards at the site.

12.2.1.4. Although not routinely performed during standard practice, immunohistochemical staining for PSMA of tumor specimens (primary and lymph node metastases) may be performed, although not required.

12.2.1.5. All regions not sampled for biopsy/histopathology will be designated as indeterminate for disease by pathology. Conventional imaging follow-up may be used in these cases to determine tissue status.

12.2.2. Follow-up Imaging will be used as a secondary assessment for prostate cancer in the event pathology information is not available:

All subjects will be tracked for follow-up conventional imaging between 3-12 months post  $^{68}\text{Ga}$ -PSMA-HBED-CC (dedicated CT, MRI and/or bone scan) as per site standard of care. If no follow-up imaging has been performed within the 9 months following the  $^{68}\text{Ga}$ -PSMA-HBED-CC scan, then the research study will pay for an additional follow-up CT scan to be performed in the 9-12

month window post-Ga-PSMA-HBED-CC scan. Follow up imaging will only be performed on subjects that have positive Ga-PSMA-HBED-CC findings because conventional imaging assessment for disease is primarily targeting suspicious lesions identified by Ga-PSMA-HBED-CC PET/CT. Interpretation of follow-up imaging will be performed by local read. Preferably, the follow-up conventional imaging should be the same modality/modalities as the initial staging work-up to allow for reproducible and accurate comparisons. Conventional imaging standards as described below will be used to determine tissue positive for prostate cancer disease. Conventional imaging will not be used to determine negative prostate cancer disease regions due to its inherently low negative predictive value.

Tissue positive for prostate cancer disease based on follow-up imaging:

12.2.2.1. Lymph nodes will be assessed by change in size.

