  - If PSA increases by more than 25% (PCWG3 definition of recurrence) on systemic therapy, then an increase in the size of lesion by more than 20% in the long axis diameter will be considered positive for disease.
- b. In subjects with localized suspected lesions(s) receiving targeted treatment without concomitant systemic treatment there are two ways to meet positive disease criteria:
  - If the subject demonstrates a decrease of PSA by greater than 50% after targeted treatment [OR]
  - If on post-treatment follow-up imaging within 3-12 months, lesions seen on CT or MRI decrease by more than 30% in long axis diameter (with a minimum of 3 mm in change in size)
- c. For untreated subjects: If on follow-up imaging within 3-12 months, lesions seen on CT or MRI increase by more than 20%

in long axis diameter (with a minimum of 3 mm in change in size).

ii. Negative for disease:

- Conventional Imaging follow up will not be used for assessment of negativity for disease

iii. Indeterminate for disease

- Regions with no visceral lesions determined to be positive by the conventional imaging criteria described above and without pathology will be designated as visceral regions indeterminate for prostate cancer disease.
- Prostate bed and prostate regions not determined to be positive by the conventional imaging criteria described above and without pathology will be designated as prostate regions indeterminate for prostate cancer disease.
- Subjects that have had neither pathology sampling, nor conventional imaging follow up will have all prostate and visceral regions designated as indeterminate for disease by reference standard.

12.2.2.3. Bone lesions will be considered:

i. Positive for disease on baseline assessment:

- Any positive sclerotic lesion on the CT portion of the Ga-PSMA-HBED-CC PET or on a separate CT obtained  $\leq$  30 days before or after the PET/CT.
- Focal uptake on the baseline bone scan performed within one month of Ga-PSMA-HBED-CC PET.
- Any MRI lesion in bone read as positive on the initial MRI performed within one month of Ga-PSMA-HBED-CC PET.

ii. Positive for disease on follow up:

- Any new positive sclerotic lesion on CT within 12 months of Ga-PSMA-HBED-CC PET scan
- Any new MRI bone lesion within 12 months of Ga-PSMA-HBED-CC PET scan
- Any new focal uptake in bone within 12 months of Ga-PSMA-HBED-CC PET scan

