13.3.2. True negative region

13.3.2.1.  **$^{68}\text{Ga}$  PSMA-HBED-CC PET negative for extra-pelvic node metastases by internal blind reader** – and pathology (if available) negative for disease, and, extra-pelvic node not positive for disease by imaging.

13.3.2.2.  **$^{68}\text{Ga}$  PSMA-HBED-CC PET negative for visceral metastases by internal blind reader** – and pathology (if available) negative for disease, and, visceral lesion not positive for disease by imaging.

13.3.2.3.  **$^{68}\text{Ga}$  PSMA-HBED-CC PET negative for osseous metastases by internal blind reader** - and pathology (if available) negative for disease, and, osseous lesion not positive for disease by imaging.

13.3.3. False positive region:

13.3.3.1.  **$^{68}\text{Ga}$  PSMA-HBED-CC PET positive for extra-pelvic nodes by internal blind reader**, pathology (if available) is negative, and imaging after prostatectomy demonstrates that node is not positive for disease.

13.3.3.1.1.  **$^{68}\text{Ga}$  PSMA-HBED-CC PET positive for regional node by internal blind reader**, but pathology (if available) is positive for node but in a different nodal region than the node seen on PSMA PET.

13.3.3.2. **PSMA-HBED-CC PET positive for visceral lesion by internal blind reader**, pathology (if available) is negative, and imaging after prostatectomy demonstrates that the visceral lesion is not positive for disease.

13.3.3.2.1.  **$^{68}\text{Ga}$  PSMA-HBED-CC PET positive for visceral lesion by internal blind reader**, but pathology (if available) is positive for visceral lesion but in a different region than the visceral region seen on PSMA PET.

13.3.3.3.  **$^{68}\text{Ga}$  PSMA-HBED-CC PET positive for osseous lesion by internal blind reader**, pathology (if available) is negative, and imaging after prostatectomy demonstrates that the osseous lesion is not positive for disease

13.3.3.3.1.  **$^{68}\text{Ga}$  PSMA-HBED-CC PET positive for osseous lesion by internal blind reader**, but pathology (if available) is positive for osseous lesion but in a different region than the osseous region seen on PSMA PET.

13.3.4. False negative region:

13.3.4.1.  **$^{68}\text{Ga}$  PSMA-HBED-CC PET negative for extra-pelvic nodes**

by internal blind reader, and pathology (if available) positive for that node, or, extra-pelvic node positive for disease by imaging as defined in Section 12.2.2.1.

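### The secondary region rules in 13.3 do not follow the pathology-first standard of 12.2, so a PET-positive lesion with decisive negative pathology but positive follow-up imaging is not scored as the false positive it should be

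*Combined protocol and SAP*

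**What the plan says.** **Reference standard (12.2).** Section 12.2.1 ranks histopathology first. For nodes and visceral lesions, 12.2.1.2 says that when the PET-positive tissue itself was biopsied, "a negative pathologic finding of the biopsied tissue is considered negative for disease". For bone, 12.2.1.3 sends negative biopsies of PET-positive lesions for further evaluation, but settles the case where pathology shows another diagnosis known to take up the tracer ("eg Renal Cell Carcinoma metastases, Paget's disease), then this will be considered negative for disease"). Section 12.2.2 places imaging second: "Follow-up Imaging will be used as a secondary assessment for prostate cancer in the event pathology information is not available". Section 12.2 also sends some biopsied cases to imaging on purpose: targeted tissue left in place, the wrong tissue sampled, or indeterminate bone pathology.

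**Region classification (13.3).** The true-positive rules in 13.3.1 require a positive PET and then, for nodes, "and pathology (if available) positive for that node, or, extra-pelvic node positive for disease by imaging as defined in Section 12.2.2.1"; for visceral lesions, "and pathology (if available) positive for that visceral lesion, or, visceral lesion positive for disease by imaging as defined in Section 12.2.2.2"; for bone, "and pathology (if available) positive for that osseous lesion, or, osseous lesion" meeting the imaging criteria of 12.2.2.3. The false-negative rules in 13.3.4 repeat this for PET-negative findings. The false-positive rules in 13.3.3.1 to 13.3.3.3 require pathology, if any, to be negative and add a second condition, for bone that "imaging after prostatectomy demonstrates that the osseous lesion is not positive for disease". The true-negative rules in 13.3.2 likewise require both.

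**The concern.** The two sections assign status differently when pathology and imaging disagree. In 12.2 a decisive pathology result ends the matter. In 13.3 a positive on either source is enough for disease, and absence of disease needs both sources to agree. The rules that produce the secondary results therefore do not implement the standard that they cite.

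At stake are sensitivity, specificity, PPV and NPV for extra-pelvic nodal, visceral and osseous metastases, which make up the whole secondary objective (1.2.1). Few such regions are likely in men selected for planned prostatectomy, so one reclassified region can move a percentage a long way. Section 2.4 says the data are meant to support further approvals of the agent, and 13.1 says they will inform a larger study.

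**Working it through.** **The plan's own figure.** The only statistical figure is the half-width table in 13.1. It reproduces: at 80%, 1.96 × √(0.80 × 0.20 / 30) = 14.3%. It does not bear on this point, and nothing below changes it.

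**Step 1: classify each combination.** *Decisive* pathology means a result on the correct node or visceral tissue, a positive bone result, or a bone biopsy showing an alternative diagnosis. Imaging means follow-up imaging. I read 13.3.4.2 and 13.3.4.3 as PET-negative for the visceral or osseous lesion, although both name extra-pelvic nodes.

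| PET | Decisive pathology | Imaging | 12.2 | 13.3 literal | 13.3, imaging as fallback only |
|---|---|---|---|---|---|
| + | positive | either | TP | TP | TP |
| + | negative | positive | **FP** | **TP** | **non-evaluable** |
| + | negative | not positive | FP | FP | FP |
| − | positive | either | FN | FN | FN |
| − | negative | positive | **TN** | **FN** | **non-evaluable** |
| − | negative | not positive | TN | TN | TN |

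The second row is non-evaluable on the fallback reading because 13.3.3 still demands imaging that is not positive, so the lesion meets neither rule and falls to 13.3.5.1.

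**Step 2: bone lesions sclerotic at baseline.** Section 12.2.2.3.i counts as positive "Any positive sclerotic lesion on the CT portion of the" PET, with no exception for a biopsy-proven alternative diagnosis. Take a PET-positive lesion biopsied as Paget's disease and sclerotic only on that CT. Read literally, 13.3.1.3 makes it a true positive. But 12.2.2.3.ii requires a *new* finding on follow-up, so imaging after prostatectomy can show it as not positive, and 13.3.3.3 is then met as well. The classes overlap. On the fallback reading this lesion is simply a false positive, as in 12.2.

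**Step 3: size, with assumed counts.** The documents give no lesion frequencies. One lesion per region is assumed.

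*Four PET-positive regions, one with decisive negative pathology and positive follow-up imaging:*
- 12.2: PPV = 3/4 = 75%
- 13.3 literal: 4/4 = 100%
- 13.3 fallback: 3/3 = 100%

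*With two PET-positive regions, one of them affected:* 1/2 = 50% under 12.2, against 2/2 or 1/1 = 100%.

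*All four measures.* Assume TP 6, FP 4, FN 2, TN 8 under 12.2. Here sensitivity is TP/(TP+FN); the formula printed in 13.1 has FP in the denominator, which is a separate matter.

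| Case | PPV | Sensitivity | Specificity | NPV |
|---|---|---|---|---|
| 12.2 | 6/10 = 60.0% | 6/8 = 75.0% | 8/12 = 66.7% | 8/10 = 80.0% |
| 1 PET+ region affected, literal | 7/10 = 70.0% | 7/9 = 77.8% | 8/11 = 72.7% | 80.0% |
| 1 PET+ region affected, fallback | 6/9 = 66.7% | 75.0% | 8/11 = 72.7% | 80.0% |
| 3 PET+ regions affected, literal | 9/10 = 90.0% | 9/11 = 81.8% | 8/9 = 88.9% | 80.0% |
| 3 PET+ regions affected, fallback | 6/7 = 85.7% | 75.0% | 8/9 = 88.9% | 80.0% |
| 1 PET− region affected, literal | 60.0% | 6/9 = 66.7% | 7/11 = 63.6% | 7/10 = 70.0% |
| 2 PET− regions affected, literal | 60.0% | 6/10 = 60.0% | 6/10 = 60.0% | 6/10 = 60.0% |

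**The case against.** The strongest reply is that 13.3 never sets out to override pathology. Each true-positive rule qualifies pathology as *if available* and cites a subsection of 12.2.2, whose opening restricts imaging to cases without pathology. Read that way, the *or* is a fallback. This is a fair reading, and it removes the inflation of sensitivity. It does not rescue the false-positive rules, which add an imaging condition on top of negative pathology; the second row of the table then becomes non-evaluable and still leaves the PPV and specificity denominators. The primary endpoint has the guard that is missing here: 13.2.1.2 scores a pathology-negative patient as a true positive only if imaging shows that the node was not removed.

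The second reply is that the conflict is narrow, and that stands. Resected tissue cannot change size, so for nodes and visceral lesions it takes a correctly targeted negative needle biopsy with tissue left in place that later meets the size criteria. Biopsy is discretionary (5.7.3), known Paget's disease is excluded (3.2.4), and 12.2.2 confines follow-up imaging to men with positive PET findings, which further limits the PET-negative route.

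Three stronger conclusions might be inferred and are not supported:
- *That all these rules turn benign lesions into PET successes.* The false-negative rules apply only to PET-negative findings, where an override creates a PET miss.
- *That a baseline-sclerotic Paget lesion can never be a false positive.* Step 2 shows that it can.
- *That 12.2 treats every negative biopsy as benign.* A negative bone biopsy without an alternative diagnosis goes to further evaluation by design.

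**Conclusion.** Wrong as written, for the descriptive secondary endpoints only. When decisive pathology is negative and follow-up imaging is positive, 13.3 gives a class other than the one 12.2 requires.

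- **PET-positive lesions:** PPV and specificity are biased upward on either reading of 13.3; sensitivity is biased upward on the literal reading only.
- **PET-negative lesions:** on the literal reading a 12.2 true negative becomes a false negative, which lowers sensitivity and NPV. The net direction for sensitivity and specificity therefore depends on how many regions fall on each side.
- **Bone lesions with an alternative diagnosis, sclerotic only at baseline:** the literal true-positive and false-positive rules can both apply.

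The direction for each route follows from the text. The size does not: 75% against 100% rests on an assumed single affected region among four. The primary endpoint and the sample size of 30 are untouched, and 13.3 plans no significance testing, so it would go too far to say that the trial's main conclusion is at risk.

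**What to change.** State in 13.3.1 to 13.3.4 that region status is the status assigned under 12.2, and edit the rules to match:

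1. **Limit imaging** to cases where 12.2.1 gives no decisive pathology result: no pathology; targeted tissue not removed or wrong tissue biopsied; or a bone biopsy that is indeterminate, or negative without an alternative diagnosis (12.2.1.3). Naming the plainly negative bone biopsy matters, because it would otherwise have no class when imaging is positive.
2. **Let decisive negative pathology stand alone.** Where node or visceral pathology of the correct tissue is negative, or bone pathology shows an alternative diagnosis, score a PET-positive lesion as false positive and a PET-negative lesion as true negative, with no imaging condition. This also removes the need for imaging after prostatectomy in men who do not have surgery, a situation that 13.2.5.2 foresees.

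The cost is wording, with no new data, and PPV may come out slightly less favourable. One consequence needs an explicit decision. Regions with no pathology and no positive imaging are true negatives or false positives in 13.3 but indeterminate in 12.2. Adopting the 12.2 status to the letter would make them non-evaluable and could leave few regions for specificity and NPV. That is a separate question, and the edit should say how such regions are handled. The changes should be made before regions are classified.

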13.3.2. True negative region

13.3.2.1.  **$^{68}\text{Ga}$  PSMA-HBED-CC PET negative for extra-pelvic node metastases by internal blind reader** – and pathology (if available) negative for disease, and, extra-pelvic node not positive for disease by imaging.

13.3.2.2.  **$^{68}\text{Ga}$  PSMA-HBED-CC PET negative for visceral metastases by internal blind reader** – and pathology (if available) negative for disease, and, visceral lesion not positive for disease by imaging.

13.3.2.3.  **$^{68}\text{Ga}$  PSMA-HBED-CC PET negative for osseous metastases by internal blind reader** - and pathology (if available) negative for disease, and, osseous lesion not positive for disease by imaging.

13.3.3. False positive region:

13.3.3.1.  **$^{68}\text{Ga}$  PSMA-HBED-CC PET positive for extra-pelvic nodes by internal blind reader**, pathology (if available) is negative, and imaging after prostatectomy demonstrates that node is not positive for disease.

13.3.3.1.1.  **$^{68}\text{Ga}$  PSMA-HBED-CC PET positive for regional node by internal blind reader**, but pathology (if available) is positive for node but in a different nodal region than the node seen on PSMA PET.

13.3.3.2. **PSMA-HBED-CC PET positive for visceral lesion by internal blind reader**, pathology (if available) is negative, and imaging after prostatectomy demonstrates that the visceral lesion is not positive for disease.

13.3.3.2.1.  **$^{68}\text{Ga}$  PSMA-HBED-CC PET positive for visceral lesion by internal blind reader**, but pathology (if available) is positive for visceral lesion but in a different region than the visceral region seen on PSMA PET.

13.3.3.3.  **$^{68}\text{Ga}$  PSMA-HBED-CC PET positive for osseous lesion by internal blind reader**, pathology (if available) is negative, and imaging after prostatectomy demonstrates that the osseous lesion is not positive for disease

13.3.3.3.1.  **$^{68}\text{Ga}$  PSMA-HBED-CC PET positive for osseous lesion by internal blind reader**, but pathology (if available) is positive for osseous lesion but in a different region than the osseous region seen on PSMA PET.

13.3.4. False negative region:

13.3.4.1.  **$^{68}\text{Ga}$  PSMA-HBED-CC PET negative for extra-pelvic nodes**

by internal blind reader, and pathology (if available) positive for that node, or, extra-pelvic node positive for disease by imaging as defined in Section 12.2.2.1.

13.3.4.2.  **$^{68}\text{Ga}$  PSMA-HBED-CC PET negative for extra-pelvic nodes by internal blind reader**, and pathology (if available) positive for that visceral lesion, or, visceral lesion positive for disease by imaging as defined in Section 12.2.2.2.

13.3.4.3.  **$^{68}\text{Ga}$  PSMA-HBED-CC PET negative for extra-pelvic nodes by internal blind reader**, and pathology (if available) positive for that osseous lesion, or, osseous lesion positive for disease by imaging as defined in Section 12.2.2.3.

13.3.5. Non-evaluable region:

13.3.5.1. Any region that does not have sufficient data to meet the criteria for definition of true positive region, true negative region, false positive region, or false negative region will be classified as non-evaluable.

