## 1. OBJECTIVES

### 1.1. Primary objective

- 1.1.1. Determine sensitivity, specificity, positive, and negative predictive value of  $^{68}\text{Ga}$  PSMA-HBED-CC PET for detection of regional pelvic nodal metastases compared to pathology at radical prostatectomy (per patient, using nodal regional correlation).

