#### 13.2.3. False positive patient:

13.2.3.1. **Ga PSMA-HBED-CC PET/CT positive for regional nodes**

**by internal blind reader**, pathology at prostatectomy is negative, and imaging after prostatectomy demonstrates that node is no longer present as defined in Section 12.2.1.2.

13.2.3.2.  **$^{68}\text{Ga}$  PSMA-HBED-CC PET/CT positive for regional node by internal blind reader**, but pathology at prostatectomy is positive for node but in a different nodal region than the node seen on PSMA PET.

13.2.4. False negative patient:

13.2.4.1.  **$^{68}\text{Ga}$  PSMA-HBED-CC PET/CT negative for regional nodes by internal blind reader**, but pathology at prostatectomy is positive for regional nodes.

13.2.5. Non-evaluable patient:

13.2.5.1. Any subject that does not have sufficient data to meet the criteria for definition of true positive patient, true negative patient, false positive patient, or false negative will be classified as non-evaluable.

13.2.5.2. Patients with extrapelvic nodal metastases will not be included in this analysis for the primary endpoint if patients do not undergo prostatectomy.

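### The extra-pelvic false-positive sub-rule 13.3.3.1.1 is written for a regional (pelvic) node, and none of the three mismatch rules requires the PET-positive region itself to be reference-negative

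*Combined protocol and SAP*

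**What the plan says.** Section 13.3 introduces its classification rules as covering extra-pelvic nodal, visceral and osseous metastases. It plans to report accuracy for those three classes and also over all imaged regions.

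The false-positive rule for nodes, 13.3.3.1, applies when the scan is "PET positive for extra-pelvic nodes by internal blind reader", pathology (where there is any) is negative, and later imaging does not show the node to be diseased. Its sub-rule 13.3.3.1.1 has a different condition, "PET positive for regional node by internal blind reader", combined with "pathology (if available) is positive for node but in a different nodal region than the node seen on PSMA PET".

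The visceral sub-rule 13.3.3.2.1 reads "pathology (if available) is positive for visceral lesion but in a different region than the visceral region seen on PSMA PET", and the osseous sub-rule 13.3.3.3.1 reads "pathology (if available) is positive for osseous lesion but in a different region than the osseous region seen on PSMA PET". The primary-endpoint rule 13.2.3.2 reads "pathology at prostatectomy is positive for node but in a different nodal region than the node seen on PSMA PET".

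The primary objective, 1.1.1, concerns "regional pelvic nodal metastases compared to pathology at radical prostatectomy". Section 5.6.2 likewise speaks of regional nodes as pelvic.

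**The concern.** A classification rule for a secondary endpoint defined outside the pelvis is triggered by a finding inside it. If an analyst applies it as written, a pelvic PET finding whose positive pathology lies in another nodal region enters the extra-pelvic table as an error, although the patient may have no extra-pelvic finding. Few extra-pelvic positives can be expected among 30 patients, so a single such entry could visibly change the reported PPV.

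The second problem is shared by all three mismatch rules. They look at where pathology was positive and are silent on the reference status of the region that PET called positive. A region with no reference result, or one already confirmed by imaging, could be counted against PET because a different site was biopsied and found positive.

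**Working it through.** The plan gives no figure for this point, so the check is mainly a comparison of rules.

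**1. What the regional-node condition means.** In 1.1.1, in 5.6.2 and throughout 13.2, regional nodes are pelvic. No text gives the term another meaning in 13.3.3.1.1. The other extra-pelvic nodal rules (13.3.1.1, 13.3.2.1, 13.3.3.1, 13.3.4.1) all name extra-pelvic nodes. The visceral and osseous sub-rules repeat their parent's lesion type. Rule 13.3.3.1.1 nearly repeats 13.2.3.2, with the reference to prostatectomy replaced by the if-available qualifier. Rules 13.3.4.2 and 13.3.4.3 contain a similar slip: they are false-negative rules for visceral and osseous lesions but carry a PET condition about extra-pelvic nodes. Uncorrected copying is the likely cause.

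**2. Three ways to read 13.3.3.1.1.**

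- *Literally.* A pelvic mismatch is a false positive under the extra-pelvic heading. A patient with no extra-pelvic finding could at the same time meet the extra-pelvic true-negative rule, 13.3.2.1.
- *Limited by its parent.* No node is both pelvic and extra-pelvic, so the rule is empty. An extra-pelvic location mismatch then has no rule, although visceral and osseous mismatches do.
- *Meant for the all-regions summary.* The text does not say so. Section 13.3 has no pelvic true-positive, true-negative or false-negative rule, so pelvic nodes would enter that summary only as errors.

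**3. The missing condition in the three mismatch rules.** Section 12.2.1.5 makes a region without tissue sampling indeterminate by pathology and lets follow-up imaging settle it. Rule 13.3.5.1 makes a region non-evaluable only if no other category fits. A mismatch rule that ignores the region's own status can fit first and so pre-empt 13.3.5.1. It can also collide with a true-positive rule. Suppose PET is positive in the spine and a sclerotic lesion on the baseline CT makes it positive under 12.2.2.3: that is a true positive under 13.3.1.3. If a biopsy is positive only in a rib, 13.3.3.3.1 can also call the spine finding a false positive. If the sub-rules were instead held to inherit every condition of their parents, they would add nothing, because the parent alone would already give a false positive.

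**4. Size, by illustration.** The counts are assumed. PPV = TP/(TP + FP); specificity = TN/(TN + FP). There are no other false positives, and one misplaced case is added.

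| Assumed count | Before | After one misplaced case |
|---|---|---|
| TP = 2 | PPV 2/2 = 100% | 2/3 = 67% |
| TP = 3 | PPV 3/3 = 100% | 3/4 = 75% |
| TN = 10 | specificity 10/10 = 100% | 10/11 = 91% |
| TN = 28 | specificity 28/28 = 100% | 28/29 = 97% |

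If the case is moved out of the true negatives rather than added, specificity is 9/10 = 90% or 27/28 = 96%, which is little different.

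**5. What is not touched.** The precision table in 13.1 follows from 1.96 × √(p(1 − p)/30). For p = 0.70, 0.75, 0.80, 0.85 and 0.90 this gives 16.40, 15.49, 14.31, 12.78 and 10.74 percentage points, matching the printed values. It uses none of the rules in 13.3. The primary endpoint is classified under 13.2, where the word regional is correct.

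**The case against.** The strongest reply is that nobody would apply the rule literally. The lead-in to 13.3 limits the rules to sites outside the pelvis, the sub-rule is numbered under an extra-pelvic parent, and Table 12-2 places obturator and iliac nodes in Region 2 and abdominal and thoracic nodes in Region 3. Section 12 derives final results from those sub-regions, so a pelvic finding has no obvious path into Region 3. This stands as far as it goes: a reader might infer that pelvic mismatches will certainly contaminate the extra-pelvic results, and the documents do not support that certainty. It does not save the rule, because read this way the rule is empty.

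A right versus left obturator mismatch is a tempting example but a contestable one. Both lie in Region 2, and 12.1.1.1 says that pelvic sub-region data do not feed the primary or secondary endpoints directly, whereas 5.6.3 treats left and right as separate nodal regions. The spine and rib example depends on the sub-region level in the same way, since Table 12-1 puts all bone in one region and 12.1.1.3 repeats the restriction. Yet a mismatch within bone can exist only at sub-region level, so the rules themselves presuppose it.

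A reader might also infer that counting one patient against PET in both endpoints is an error. It is not in itself: the primary endpoint is per patient and the secondary is per region.

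Finally, it would be tempting to declare every unsampled region non-evaluable. That would contradict 12.2.1.5 and 13.3.1.1 to 13.3.1.3, under which imaging alone can establish disease, as well as objective 1.2.1, which names imaging follow-up as part of the reference.

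**Conclusion.** The point holds in a limited form. Rule 13.3.3.1.1 is wrong as written, and none of the three readings gives a usable extra-pelvic mismatch rule. The three mismatch rules also omit the reference status of the region being classified. Both defects can bias PPV and specificity downward. How often this would happen depends on how the analyst reads the text and on counts that the documents do not give, so the 67–75% for PPV and 91–97% for specificity are illustrations of a single misplaced case and not forecasts. The regional-node wording leaves sensitivity alone; sensitivity could change only if a region that meets a true-positive rule were scored as a false positive instead.

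The endpoint is a descriptive secondary one in a pilot without significance testing, so the consequences are modest. The correction should still be made, because these are operative rules and Section 2.4 intends the data to support further approvals.

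**What to change.** In 13.3.3.1.1, replace the regional node with the extra-pelvic node.

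In all three mismatch rules, classify each region on its own Section 12.2 reference result, whether from pathology or imaging:

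- PET-positive and reference-positive: true positive.
- PET-positive and reference-negative under the relevant 13.3.3 parent rule: false positive.
- PET-negative and reference-positive: false negative.
- Reference-indeterminate, meaning that neither pathology nor imaging settles it: non-evaluable.

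A location mismatch then needs no special category: the PET-positive region and the pathology-positive region are each scored separately. State whether a region here means a Table 12-1 region or a Table 12-2 sub-region.

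If pelvic nodes are meant to enter the all-regions summary, say so separately and add matching pelvic true-positive, true-negative, false-positive and false-negative rules. Rule 13.2.3.2 needs no change on this account. The PET conditions in 13.3.4.2 and 13.3.4.3 can be corrected in the same edit.

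The cost is a wording change in Section 13.3, with no additional patients, scans or data.
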